#### Per-Protocol Population

The per protocol (PP) population excludes subjects with significant protocol deviations and excludes any incomplete subject data. Protocol deviations will be assessed by the clinical team, prior to database lock. Efficacy analyses will be performed on the PP population with observed data only.

**Sample Size**

33 subjects.

**Efficacy Analyses**

The continuous and ordinal efficacy variables collected at each visit (and time point, where relevant) will be summarized with number of observations (n), mean, standard deviation, median, minimum and maximum. Statistical inference testing will be conducted and the results will be utilized as additional descriptors of the data. Two-sample *t*-tests will be employed for continuous variables. Two-sample *t*-tests, Wilcoxon rank sum tests and analysis of covariance (ANCOVA) models adjusting for baseline will be employed for ordinal variables. For the ANCOVA models, treatment will be compared to the placebo. Pearson's chi-square or Fisher's exact tests (in the case of expected counts less than 5) will be employed for qualitative variables. Where appropriate, the change from baseline for each parameter will also be summarized using descriptive statistics.

The individual symptoms collected in the diary will be analyzed including all data across the 70-day treatment period, testing for a treatment effect using a generalized linear model that accounts for repeated measures with an unstructured correlation structure, including terms for diary day and the treatment-by-day interaction.

**VII. RISKS AND DISCOMFORTS**

Based on the clinical use of the drug within and outside of controlled studies, there are no known risks. The amount of the active progesterone is several hundred-fold lower than the current injectable, topical, and oral forms. Skin penetration studies by Sponsor using the Franz cell has shown that less than 5% of progesterone passes through the top layer of the skin (stratum corneum).

Use of other ocular medications can continue, concurrent with use of Pro-ocular.

**VIII. POTENTIAL BENEFITS****a. Potential benefits to participating individuals**

The potential benefits to participating individuals are reduction or elimination of ocular discomfort, especially the extreme pain experienced by many ocular GvHD patients, and ocular tissue damage repair, potentially preventing progression to when surgical procedures may be required.

Another potential benefit is the reduction of use of artificial tears and other eye drops that only provide temporary relief.

There is potential improvement of the overall quality of life, and enabling the return to normal daily living, sleep, work, and other activities.

**b. Potential benefits to society**

The study is expected to prove that the study drug fulfills an unmet need for ocular GvHD treatment.

## IX. MONITORING AND QUALITY ASSURANCE

### a. Independent monitoring of source data

The sponsor intends to provide independent monitoring to ensure all data are collected, and entered into a database accurately.

### b. Safety monitoring

A Safety Management Plan is provided to clinical management personnel. A 24-hour telephone physician safety monitor line will be provided for the subjects to call.

### c. Outcomes monitoring

Data will be analyzed by a third-party statistical group.

### d. Adverse event reporting guidelines

All adverse events will be collected, whether potentially related or unrelated to study drug use. The adverse events will be categorized according to the latest version of MedDRA (Medical Dictionary for Regulatory Activities) using Common Terminology Criteria (CTCAE). The Safety Management Plan provides guidance for what is considered a serious adverse event, the forms to be completed in such cases, and when a serious adverse event needs to be reported to the FDA.

## APPENDICES

## SCHEDULE OF VISITS AND ASSESSMENTS

## Visits 1-7

Blue = Conducted at DFCI		Study Treatment Phase					Placebo Cross-over Phase	
Black = Conducted at MEEI	Visit 1 (Screening)	Visit 2 Baseline & First Drug Application		Visit 3	Visit 4	Visit 5	Visit 6	Visit 7
	Day -14 to -1	Day 1	Day 1	Day 14±2	Day 42±3	Day 70±3	3 weeks	6 weeks
Procedure		Pre-Dose	30-60 min Post-Dose					
2-digit screening number	X							
Informed consent	X							
Visual acuity (current correction)	X					X		
NIH Ocular GvHD Score	X					X		X 
Facial photo		X				X		X
Slit lamp biomicroscopy	X			X	X	X	X	X
Undilated fundoscopy exam	X					X		
Corneal and conjunctival staining	X			X	X	X	X	X
Intraocular pressure	X					X		X
Inclusion/Exclusion criteria	X							
Medical/Ophthalmology history and updates	X	X		X	X	X	X	X
Prior and concomitant medication query	X	X		X	X	X	X	X
Concomitant medications (BMT)	X				X	X		X
Medical history & physical (BMT)	X							
Demographic data	X							
Video of face & eyes (1 minute)		X	X	X	X	X	X	X
TearScan examination		X	X	X	X	X	X	X
Urine pregnancy test	X					X		
Modified SANDE questionnaire	X			X	X	X	X	X
GLIA Ocular Surface Disease Symptoms Questionnaire	X	X	X	X	X	X	X	X
Adverse event query			X	X	X	X	X	X
Screen Pass/Fail	X							
3-digit random number	X							
BMT systemic evaluation & GvHD assessment	X				X	X		X
Standard GvHD, CBC, and metabolic labs	X				X	X		X
Endocrine panel	X				X	X		X
Daily diary and ocular medication log collected				X	X	X	X	X
Study drug collected/ accountability				X	X	X	X	X
Study drug application (in-clinic)		X						
Study drug dispensed		X		X	X	X	X	
Daily diary & ocular medication log dispensed			X	X	X	X	X	

 Added as protocol deviation to original protocol v4.

## SCHEDULE OF VISITS AND ASSESSMENTS

### Visits 8-9 Long Term Open Label

Blue = Conducted at DFCI	Visit 8	Visit 9
Black = Conducted at MEEI	66 ± 6 weeks (15 months)	117 ± 6 weeks (27 months)
Procedure		
Informed consent for long term open phase	X	X
Visual acuity (current correction)	X	X
NIH Ocular GvHD Score	X	X
Facial photo	X	X
Slit lamp biomicroscopy	X	X
Undilated fundoscopy exam	X	X
Corneal and conjunctival staining	X	X
Intraocular pressure	X	X
Ophthalmology updates	X	X
Concomitant medications (BMT)	X	X
Video of face & eyes (1 minute)	X	X
TearScan examination	X	X
Urine pregnancy test	X	X
Modified SANDE questionnaire	X	X
GLIA Ocular Surface Disease Symptoms Questionnaire	X	X
Adverse event query	X	X
BMT systemic evaluation & GvHD assessment	X	X
Standard GvHD, CBC, and metabolic labs	X	X
Endocrine panel	X	X

Initials: \_\_\_\_\_ Subject #: \_\_\_\_\_ Date: \_\_\_\_\_ Examiner: \_\_\_\_\_

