## SYNOPSIS

Protocol Title:	Treatment safety and efficacy using Pro-ocular™ for chronic ocular graft versus host disease (GvHD) following allogeneic hematopoietic stem cell transplantation
Version / Date:	V 5.1 March 17, 2020
Protocol Number:	oGvHD-1
Study Phase:	2
Study Drug and Placebo:	Pro-ocular™ 1% topical gel (progesterone USP) and placebo
IND Number:	143010
Indication:	Reduce or eliminate ocular symptoms and signs of chronic ocular graft-versus-host disease
Study Objective:	To evaluate the safety and efficacy of Pro-ocular™ 1% topical gel administered twice daily for 70 days in ameliorating symptoms and signs of chronic ocular GvHD.
Design Structure:	Single center, randomized, parallel, double-masked, placebo-controlled study
Institutional Review Board:	Partners Human Research Committee
Duration:	10-week treatment period (active and placebo) 6-week crossover period (placebo to active) open label long term phase to extend the entire treatment period for 27 months
Dosage/Dose Regimen:	Approximately 0.07 g Pro-ocular™ 1% topical gel applied and massaged into the forehead skin twice daily, morning and before bedtime.
Route of Administration:	
Visit Schedule, Double-Masked Phase:	5 visits over 70 days including: 
 
Visit 1, Screening (Day -14 to -1)
 
Visit 2, Baseline and 1st drug application
 
Visit 3, 2-week follow-up (Day 14 ± 2)
 
Visit 4, 6-week follow-up (Day 42 ± 3)
 
Visit 5, 10-week follow-up (Day 70 ± 3)
 

Crossover Phase for Subjects on Placebo:	Subjects in placebo group will receive Pro-ocular 1% topical gel for twice daily administration for over 6 weeks starting at Visit 5:

	
 
• Visit 6, 13-week follow-up (3 weeks on active drug), placebo cross-over subjects only
 
• Visit 7, 16-week follow-up (6 weeks on active drug), placebo cross-over subjects only
 

Long Term Follow Up for Subjects in Open Label Phase (for Eligible & Interested Subjects)	Drug will be supplied after the study period for a total of 27 months' treatment period beginning with Visit 2, with safety monitoring and reporting by the PI and co-investigators under protocol during clinic: Visit 8, 66 ± 6 weeks (15 months) Visit 9, 117 ± 6 weeks (27 months)

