## V. STUDY PROCEDURES

The sequence of procedures at each clinic visit is as follows:

Visit 1 (Day -14 to -1)
Screening
Ophthalmology assessment
Informed consent by investigator
2-digit subject ID number
GLIA Ocular GvHD symptoms questionnaire
SANDE symptoms questionnaire
NIH Ocular GvHD score
Visual acuity with current correction
Slit-lamp biomicroscopy
Undilated fundoscopy exam
Corneal and conjunctival staining
Intraocular pressure
Urine pregnancy testing (as needed)
Inclusion/Exclusion criteria

Drug collection & accountability
 
1 minute video of face and eyes (+ blink interval)
 
TearScan examination
 
Adverse event query
 
SANDE symptoms questionnaire
 
GLIA Ocular GvHD symptoms questionnaire
 
Slit-lamp biomicroscopy
 
Corneal and conjunctival staining
 
Study drug, daily diary and ocular medication log dispensed

BMT(DFCI) physician systemic evaluation
Standard lab tests, GvHD assessment
↓
Visit 5 (Day 70 ± 3), 10 weeks' treatment
Ophthalmology assessment

Visual acuity
 
Medical and medication update
 
Diary and ocular medication collection & compliance
 
Drug collection & accountability
 
Urine pregnancy test if applicable
 
Facial photo
 
1 minute video of face and eyes (+ blink interval)
 
TearScan examination
 
Adverse event query
 
SANDE symptoms questionnaire
 
GLIA Ocular GvHD symptoms questionnaire
 
Slit-lamp biomicroscopy
 
Undilated fundoscopy exam
 
Corneal and conjunctival staining
 
NIH Ocular GvHD score
 
Intraocular pressure
 
Urine pregnancy test
 
End of study phase
 
Reconfirm drug dispensing for Open label Phase
 
Dispense diary, ocular medication log and drug to Placebo group

BMT (DFCI) physician systemic evaluation
Concomitant medications
Laboratory tests, standard & endocrine panel
GvHD assessment
↓
Visit 6, 13 weeks for Placebo group only

Medical and medication update
 
Diary and ocular medication log collection & compliance
 
Drug collection & accountability
 
1 minute video of face and eyes (+ blink interval)
 
TearScan examination
 
Adverse event query
 
SANDE symptoms questionnaire

GLIA Ocular GvHD symptoms questionnaire
Slit-lamp biomicroscopy
Corneal and conjunctival staining
↓
Visit 7, 16 weeks for Placebo group only
Facial photo

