#### 4.2 Masking and Unmasking

During the Study Treatment Phase of the study (Visit 1 – Visit 5), the subject, Investigator, and study staff will be masked.

For each randomization number, the Sponsor will label each of a set of 11 study drug pouches prominently with the 3-digit randomization code followed by container number.

e.g.

Pouch #1, #2, and #3 will be labeled xxx-1, xxx-2 and xxx-3 for dispensing at Visit 2 Day 1 Baseline.

Pouch #4, 5, 6, and 7 will be labeled xxx-4, -5, -6, and -7 for dispensing at Visit 3 Day 14.

Pouch #8, 9, 10, and 11 will be labeled xxx-8, -9,-10 and -11 for dispensing at Visit 4 Day 42

Open label pouches will be supplied for Visit 5 (3 pouches active), and Visit 6 (3 pouches).

Note: Rarely a tube may fail to pump due to airlock. Therefore an extra tube is provided each time to ensure there will be sufficient product. (Each tube dispenses approximately 24 doses.)

The Sponsor is responsible for emergency unmasking as needed.

For each subject, after the completion of all Visit 5 assessments, the Investigator will unmask the individual subject to determine eligibility for the Placebo Cross-over Phase. If the subject was originally randomized to Placebo, then the subject will enter the Placebo Cross-over Phase. If the subject was originally randomized to Pro-ocular™ 1% topical gel, then the subject's participation in the study will be complete.

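### The long-term schedule first marks its phase-specific consent at Visit 8, about 50 to 56 weeks after long-term supply appears to start, with no scheduled adverse event query in between

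*Protocol*

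**What the plan says.** **Consent.** The protocol appendix for Visits 8-9 contains the row "Informed consent for long term open phase", marked at both visits. The appendix for Visits 1-7 has a single consent row, marked at Visit 1. The Section V procedure lists for Visits 8 and 9 contain no consent step.

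**Supply.** The synopsis describes an "open label long term phase to extend the entire treatment period for 27 months" and states: "Drug will be supplied after the study period for a total of 27 months' treatment period beginning with Visit 2". It restricts the phase to subjects who qualify and wish to continue. Among the Visit 5 steps in Section V is "Reconfirm drug dispensing for Open label Phase".

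**Drug records.** The Visits 1-7 schedule has rows for study drug dispensed and for collection and accountability. The Visits 8-9 schedule has neither.

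**Adverse events.** The query is marked at Visit 2 after dosing, at Visits 3 to 7 (Visits 6 and 7 are for placebo cross-over subjects only), and then at Visits 8 and 9. Section IX.d commits the study as follows: "All adverse events will be collected, whether potentially related or unrelated to study drug use".

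**The concern.** A consent specific to a phase should come before the phase's treatment. Here the only marks for it fall well into the phase and at its end. A site that works from the schedule would supply long-term drug first and take the listed consent about a year later. The phase is optional, so agreeing to it is a separate decision that should be on record before supply.

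The same table leaves long-term exposure and safety thinly recorded. With no dispensing or accountability row, the schedule requires no record of how much drug was supplied or returned. With no query between Visit 5 or 7 and Visit 8, the schedule gives no fixed point at which events in that interval are asked about. That makes it harder to date events and relate them to exposure, which is a main purpose of a long-term safety phase.

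**Working it through.** This is calendar arithmetic on the stated visit times.

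**Inputs**
- Visit 5: Day 70 ± 3, week 10 (synopsis).
- Visit 7: week 16, with no window in the protocol (synopsis).
- Visit 8: week 66 ± 6, given as 15 months. Visit 9: week 117 ± 6, given as 27 months (synopsis and Visits 8-9 schedule).

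**Reproducing the plan's own figures.** Weeks = months × 365.25 / 12 / 7.
- 15 months: 65.2 weeks, against the stated 66.
- 27 months: 117.4 weeks, against the stated 117.

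The stated times are consistent with 27 months counted from Visit 2.

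**When long-term supply starts.** This is an inference, because no schedule row dispenses long-term drug. Treatment counted for 27 months from Visit 2, with drug supplied after the study period, leaves no room for a drug-free interval up to Visit 8. Section V also places the open-label dispensing step at Visit 5. The start is therefore taken as week 10 for subjects first on active and as week 16 for former placebo subjects, after their six-week cross-over.

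**Gap from start of supply to first listed consent (Visit 8 week minus start week)**

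| Group | Nominal | With windows |
|---|---|---|
| First on active (from Visit 5) | 66 − 10 = 56 weeks | 60 − 73/7 = 49.6 to 72 − 67/7 = 62.4 weeks |
| Former placebo (from Visit 7) | 66 − 16 = 50 weeks | 60 − 16 = 44 to 72 − 16 = 56 weeks |

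For subjects first on active, the nominal gap is 56 / (117 − 10) = 52% of the open-label phase. The second consent mark, at week 117, falls when the 27 months end.

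**Gap between adverse event queries.** The last query before the long-term phase is at Visit 5 (first on active) or Visit 7 (former placebo), and the next is at Visit 8. The interval is therefore the same 56 or 50 weeks. From Visit 8 to Visit 9 is a further 117 − 66 = 51 weeks (111 − 72 = 39 to 123 − 60 = 63 with windows), also with no query in between.

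**Internal disagreement.** The appendix lists a consent at Visits 8 and 9, and Section V lists none at either visit. This contradiction does not depend on any inference about supply.

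**The case against.** The strongest objection is that the Visit 1 consent may already cover long-term use. The consent pages were not available, so this cannot be excluded. A reader might infer that subjects take the drug in a phase they have not agreed to. The documents do not support that. They show only that the phase-specific consent they list is scheduled after the phase appears to begin.

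The marks could also be re-consent, or a consent added by amendment for subjects already past Visit 5 or 7. The protocol is at version 5.1 and notes a change from version 4. That might explain a mark at Visit 8. It does not explain the lack of a mark at Visit 5 or 7 for later subjects, or why a row labelled as consent for the phase is marked at its end. The Visit 5 step does speak of reconfirming, which suggests an earlier confirmation, and the Visit 2 and 3 procedure lists are missing from the text available. However, that step concerns dispensing, and the full Visits 1-7 schedule shows no long-term consent.

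The start of supply is inferred. Section V names only the placebo group for drug at Visit 5, and the Visits 1-7 schedule marks no dispensing at Visit 7. This stands as a qualification, although the absent row is part of the problem. The quantity supplied at each dispensing is not stated, so nothing can be concluded about repeated resupply visits.

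A reader might also infer that long-term safety goes unmonitored. That is too strong. Transplant physicians who are co-investigators continue to follow the subjects, a telephone line is open at all hours, all adverse events are to be collected, and a separate Safety Management Plan exists that was not available. These mitigate the gap, but none is a scheduled study query. Nor does a missing schedule row prove that no supply records are kept.

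Finally, SAP section 4.2 says of subjects first on active that, after Visit 5, "then the subject's participation in the study will be complete". The SAP was written for protocol version 4.0 and stops at Visit 7, so this is a version difference and not evidence on when consent is taken.

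**Conclusion.** The point holds as a defect in the schedule. As written, the listed long-term consent comes about 56 weeks (subjects first on active) or 50 weeks (former placebo subjects) after the phase begins, or about 50-62 and 44-56 weeks with windows. The same interval has no scheduled adverse event query, and the long-term schedule has no drug dispensing, collection or accountability row. The appendix and Section V also disagree on whether any consent is taken at Visits 8 and 9.

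The lengths rest on two assumptions: that long-term supply follows directly on Visit 5 or Visit 7, and that sites follow the schedule as printed. Whether subjects had in fact already consented to long-term use is open and depends on the Visit 1 form.

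**What to change.** Reconcile the synopsis, the Section V lists and the two schedules on when long-term consent is taken relative to supply. Specifically:

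- Mark the long-term consent at Visit 5 for subjects first on active and at Visit 7 for former placebo subjects, before any long-term drug is supplied.
- Label the marks at Visits 8 and 9 as re-confirmation, and make the Section V lists agree.
- For subjects already receiving open-label drug, take the consent at the next contact.
- Add rows for study drug dispensed and for collection and accountability to the long-term schedule.
- Record an adverse event query at any contact where drug is supplied.

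The cost is a protocol amendment that adds consent marks at two visits, relabels two, and adds a few schedule rows. The query adds little where a supply contact takes place anyway. The small downside is that some subjects may decline the phase earlier than they otherwise would.

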### Symptom Assessment iN Dry Eye (SANDE) Questionnaire

PLEASE COMPLETE THE FOLLOWING QUESTIONS REGARDING THE FREQUENCY AND SEVERITY OF YOUR DRY EYE SYMPTOMS.

1. Frequency of symptoms:

Please place an 'X' on the line to indicate how often, on average, your eyes feel **dry and/or irritated**:

Left Rarely \_\_\_\_\_ All the time

Right Rarely \_\_\_\_\_ All the time

2. Severity of symptoms:

Please place an 'X' on the line to indicate how severe, on average, you feel your symptoms of **dryness and/or irritation**:

Left Very Mild \_\_\_\_\_ Very Severe

Right Very Mild \_\_\_\_\_ Very Severe

## GLIA™ OCULAR SURFACE DISEASE SYMPTOMS QUESTIONNAIRE - CLINIC RECORD

Initials: \_\_\_\_\_ Subject #: \_\_\_\_\_ Date: \_\_\_\_\_ Examiner: \_\_\_\_\_

Grade by placing X on the line from 'None' to 'Most severe'

None \_\_\_\_\_ Most

	Baseline Time: _____		Post-application 30-90 min Time: _____	
	OD	OS	OD	OS
Ocular discomfort	None _____ Most	None _____ Most	None _____ Most	None _____ Most
Dryness	None _____ Most	None _____ Most	None _____ Most	None _____ Most
Grittiness	None _____ Most	None _____ Most	None _____ Most	None _____ Most
Burning	None _____ Most	None _____ Most	None _____ Most	None _____ Most
Stinging	None _____ Most	None _____ Most	None _____ Most	None _____ Most
Foreign body sensation	None _____ Most	None _____ Most	None _____ Most	None _____ Most
Ocular pain	None _____ Most	None _____ Most	None _____ Most	None _____ Most
Conjunctival redness	None _____ Most	None _____ Most	None _____ Most	None _____ Most

Additional notes below: (Details and other ocular symptoms)

## GLIA™ OCULAR SURFACE DISEASE SYMPTOMS QUESTIONNAIRE - CLINIC RECORD

Initials: \_\_\_\_\_ Subject #: \_\_\_\_\_ Date: \_\_\_\_\_ Examiner: \_\_\_\_\_

Grade by placing X on the line from 'None' to 'Most severe'

None \_\_\_\_\_ Most

	Baseline Time: _____		Post-application 30-90 min Time: _____	
	OD	OS	OD	OS
Itching	None _____ Most	None _____ Most	None _____ Most	None _____ Most
Mucus discharge	None _____ Most	None _____ Most	None _____ Most	None _____ Most
Photophobia	None _____ Most	None _____ Most	None _____ Most	None _____ Most
Blurred or cloudy vision	None _____ Most	None _____ Most	None _____ Most	None _____ Most
Airflow sensitivity	None _____ Most	None _____ Most	None _____ Most	None _____ Most
Lid redness	None _____ Most	None _____ Most	None _____ Most	None _____ Most
Lid sticking	None _____ Most	None _____ Most	None _____ Most	None _____ Most

Additional notes below: (Details and other ocular symptoms)

## Ocular GvHD Evaluations & Scoring in clinic

Evaluation	Method	Scoring				
Pre-fluorescein stain						
Visual acuity	Eye chart, OD and OS	See below				
Slit lamp: Lids : Lid margin erythema, edema, ulceration, notches, entropion/ ectropion, trichiasis/madarosis, floppy eyelids, hordeolum; Conjunctiva : Hyperemia, cicatricial changes, pseudomembranes, chalasis; Cornea : Edema, ulcers, filamentous keratitis, thinning, corneal neovascularization, scars, conjunctival epithelium invasion, limbal thickening; Anterior chamber : Cells, flare; Lens opacity	Visual or slit lamp	
 
 None	Most severe	
 
 None	Most severe	
 
	None	Most severe	None	Most severe
None	Most severe					
None	Most severe					
Tear film evaluation + lid margin	TearScan	0,1, 2, 3				
After fluorescein stain						
Fluorescein staining	Slit lamp	
 
 None	Most severe	
 
 None	Most severe	
 
	None	Most severe	None	Most severe
None	Most severe					
None	Most severe					
Intraocular pressure	Applanation tonometry	Reading in mm Hg				

